### **6.6.2. NA Re-treatment Criteria and Monitoring after Stopping of NA**

Participants who meet the NA treatment completion criteria outlined in Section [6.6.1](#) will be monitored closely during the follow-up phase.

After stopping NA treatment, participants should be monitored as follows:

- Regular monitoring visits will be every 4 weeks during the follow-up phase in accordance with the [Schedule of Activities](#).

- A post-treatment HBV DNA value of >20,000 IU/mL should trigger re-testing of ALT/AST, HBV DNA, and total and direct bilirubin within a maximum of 7 days from receipt of the data and further repeats as necessary (ie, weekly until HBV DNA returns to <20,000 IU/mL).
- A post-treatment HBV DNA value of >2,000 IU/mL (but <20,000 IU/mL) should trigger a re-test within 14 days from receipt of the data and further repeats as necessary (ie, every other week until HBV DNA returns to <2,000 IU/mL).
- A post-treatment ALT value of >5x ULN should trigger re-testing of ALT, AST, ALP, total and direct bilirubin, INR, albumin, and HBV DNA on a weekly basis until ALT and AST levels have returned to <5x ULN.

After stopping NA treatment, participants should re-start NA treatment:

- Immediately with signs of decreasing liver function based on laboratory findings (eg, INR, direct bilirubin) or clinical assessment (eg, ascites, hepatic encephalopathy),
- Immediately with an HBV DNA value of >100,000 IU/mL (irrespective of confirmation and/or ALT increase).
- With confirmed post-treatment HBeAg seroreversion (HBeAg positive after it was negative at NA completion)
- With confirmed\* post-treatment increases in HBV DNA >2,000 IU/mL and ALT >5x ULN
- With confirmed\* post-treatment increases in HBV DNA >20,000 IU/mL.

*\* At least 4 weeks apart frequency of visits as described above*

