5.1.3. On-Treatment and Off-Treatment Period

The on-treatment period begins with the first drug intake and finishes with the maximum between:

- Last dose of NA + 2 days
- Last dose of PegIFN- α 2a +10 days
- Last dose of JNJ-3989 + 28 days

The off-treatment period starts after the end of on-treatment period and stops if the NA re-treatment starts.

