5.4.2.6. Flares

5.4.2.6.1. Definition

The criteria based on blood markers/lab tests for each of the flare types are defined as below.

1. **Virologic flare** is defined as follows:

Derivation 1. This derivation of virologic flare will be assessed only for those participants who are off-treatment and had $\text{HBV DNA} < \text{LLOQ}$ at the last observed point on-treatment.

The start date of a confirmed virologic flare is defined as the first date of two consecutive visits with $\text{HBV DNA} > 200 \text{ IU/mL}$. The end date of the same confirmed virologic flare is defined as the first date when HBV DNA value returns to $\leq 200 \text{ IU/mL}$ or the date of NA treatment restart, whichever comes first. Each virologic flare will be categorized based on the confirmed (i.e., two consecutive values) peak HBV DNA above any of the three thresholds within the start and end date of that flare as follows: 20,000 IU/mL , 2,000 IU/mL , and 200 IU/mL .

- 1 (Yes) = confirmed** $\text{HBV DNA} >$ peak threshold.
- 0 (No) = at least one off-treatment HBV DNA measurement available and not meeting the criteria of confirmed $\text{HBV DNA} >$ peak threshold.
- 2 (Not applicable) = no off-treatment HBV DNA quantitative measurements available.

Derivation 2. This derivation of virologic flare will be assessed only for those participants who are off-treatment and had $\text{HBV DNA} \geq \text{LLOQ}$ at the last observed point on-treatment.

The start date of a confirmed virologic flare is defined as the first date of two consecutive visits with HBV DNA log_{10} increase $> 1 \log_{10}$ from EOT. The end date of the same confirmed virologic flare is defined as the first date when HBV DNA log_{10} increase from end of treatment returns to $\leq 1 \log_{10}$ or the date of NA treatment restart, whichever comes first. Each virologic flare will be categorized based on the confirmed (i.e., two consecutive values) peak HBV DNA increase above any of the three thresholds within the start and end date of that flare as follows: $1 \log_{10}$, $2 \log_{10}$, $3 \log_{10}$.

- 1 (Yes) = confirmed** HBV DNA increase from EOT $>$ peak threshold
- 0 (No) = at least one off-treatment HBV DNA measurement available and not meeting the criteria of confirmed HBV DNA increase from EOT $>$ peak threshold.
- 2 (Not applicable) = no off-treatment HBV DNA quantitative measurements available.

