** Confirmed means that the criterion should be fulfilled at 2 or more consecutive time points or at the last observed time point.

2. **Off-treatment biochemical flare** is defined as follows:

The start date of a confirmed off-treatment biochemical flare is defined as the first date of two consecutive visits with ALT and/or AST $\geq 3 \times \text{ULN}$ and $\geq 3 \times \text{nadir}$ (i.e., lowest value observed up

to the start of the flare) while the participant does not receive any of the study interventions. The end date of the same off-treatment biochemical flare is defined as the first date when there is a 50% reduction from the peak ALT and/or AST level and <3 x ULN.

- 1 (Yes) = confirmed^{**} ALT and/or AST ≥ 3 x ULN and ≥ 3 x nadir (i.e., lowest value observed up to the start of the flare)
- 0 (No) = otherwise

3. On-treatment biochemical flare is defined as follows:

The start date of a confirmed on-treatment biochemical flare is defined as the first date of two consecutive visits with ALT and/or AST ≥ 3 x ULN and ≥ 3 x nadir (i.e., lowest value observed up to the start of the flare) while the participant receives any of the study interventions. The end date of the same on-treatment biochemical flare is defined as the first date when there is a 50% reduction from the peak ALT and/or AST level and <3 x ULN, regardless of stopping study interventions.

- 1 (Yes) = confirmed^{**} ALT and/or AST ≥ 3 x ULN and ≥ 3 x nadir (i.e., lowest value observed up to the start of the flare)
- 0 (No) = otherwise

4. Clinical flare is defined as follows:

A clinical flare occurs either when a virologic flare and biochemical flare overlap in time or when a biochemical flare starts within 4 weeks following the end of a virologic flare.

The start date of a clinical flare is defined as the minimum start date of the virologic flare and biochemical flare. The end date of a clinical flare is defined as the maximum end date of the virologic flare and biochemical flare, i.e., the later date between HBV DNA returns to ≤ 200 IU/mL (or ≤ 1 log₁₀) and 50% reduction from the peak ALT and/or AST level and <3 x ULN reached during the biochemical flare.

- 1 (Yes) = confirmed^{**} HBV DNA $>$ peak threshold (for derivation 1 of virologic flare) or HBV DNA increase from end of treatment $>$ peak threshold (for derivation 2 of virologic flare) and confirmed^{**} ALT and/or AST ≥ 3 x ULN and ≥ 3 x nadir (i.e., lowest value observed up to the start of the biochemical flare).

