- 0 (No) = otherwise

^{**} Confirmed means that the criterion should be fulfilled at 2 or more consecutive time points or at the last observed time point.

The virologic and clinical flares will be assessed only off-treatment, while biochemical flares will be identified on-treatment and off-treatment, respectively. On-treatment virologic flares are described as virologic HBV breakthrough in Section 5.4.2.7.

On-treatment will be defined as the time periods in which the participant receives any of the study interventions (JNJ-3989 or JNJ-6379 or NA or PegIFN- α 2a). Off-treatment will be defined as the

periods when the participants do not receive any of the study interventions (JNJ-3989, JNJ-6379, NA, and PegIFN- α 2a).

The incidence rate will be calculated and summarized for each type of on-treatment or off-treatment flares (virologic, biochemical and clinical) separately, as well as the overall incidence of participants experiencing at least one flare, regardless of type. Additionally, for each participant the total number of flares the participant experienced will be counted by type. Such counts will be used to summarize the distribution of the total number of flares by type and by study panel.

For on-treatment biochemical flares, the incidence of flares causing treatment discontinuation will be summarized. Further, for off-treatment flares, the count and percentage of participants who experienced a flare followed by NA re-treatment will be summarized by flare type. Similarly, the incidence of flares followed by the achievement of HBsAg seroclearance (at any time) will be summarized by flare type.

Flares that are associated with signs of liver decompensation will be provided in a listing.

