5.4.2.7. HBV Virologic Breakthrough

5.4.2.7.1. Definition

HBV virologic breakthrough is defined as having a confirmed on-treatment HBV DNA increase by $>1 \log_{10}$ from nadir level (lowest level reached during treatment) in participants who did not have on-treatment HBV DNA level $< \text{LLOQ}$ or a confirmed on-treatment HBV DNA level $>200 \text{ IU/mL}$ in participants who had on-treatment HBV DNA level $< \text{LLOQ}$. Confirmed HBV DNA increase/level means that the criterion should be fulfilled at 2 or more consecutive time points or at the last observed on-treatment time point.

On-treatment will be defined as the time period in which the participant receives any of the study interventions (JNJ-3989 and/or JNJ-6379 and/or NA and/or PegIFN- α 2a).

The number and proportion of participants who experience a virologic breakthrough will be summarized descriptively by analysis phase.

The number and proportion of participants who experience a virologic breakthrough followed by on-treatment biochemical flare will be summarized descriptively.

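### SAP 5.4.2.6.1 is inconsistent on what confirms a virologic flare, so a fast rebound that ends in NA restart after one high value can be coded as no flare or graded too low

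*SAP*

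**What the plan says.** SAP 5.4.2.6.1 gives the virologic flare four elements.

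- **Start:** "The start date of a confirmed virologic flare is defined as the first date of two consecutive visits with" HBV DNA above 200 IU/mL (Derivation 1) or a rise of more than 1 log10 from end of treatment (Derivation 2).
- **End:** return to the threshold "or the date of NA treatment restart, whichever comes first".
- **Grade:** each flare is "categorized based on the confirmed (i.e., two consecutive values) peak HBV DNA above any of the three thresholds within the start and end date". The cut-offs are 200, 2,000 and 20,000 IU/mL, or 1, 2 and 3 log10 in Derivation 2.
- **Yes/No flag:** uses a marked term explained in a footnote: "Confirmed means that the criterion should be fulfilled at 2 or more consecutive time points or at the last observed time point".

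The assessment period is limited: "The virologic and clinical flares will be assessed only off-treatment, while biochemical flares will be identified on-treatment and off-treatment, respectively". SAP 5.1.3 adds: "The off-treatment period starts after the end of on-treatment period and stops if the NA re-treatment starts".

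The neighbouring breakthrough rule (SAP 5.4.2.7.1) words its own last-value clause more tightly: the criterion is to be "fulfilled at 2 or more consecutive time points or at the last observed on-treatment time point".

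Protocol 6.6.2 restarts NA immediately on one HBV DNA value above 100,000 IU/mL, "irrespective of confirmation and/or ALT increase", and also immediately on evidence of worsening liver function. Its other HBV DNA routes need confirmation at least 4 weeks apart.

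**The concern.** The event that prompts immediate restart also closes the window in which the SAP looks for a confirming value. The start-date and grading sentences make no exception for this. The footnote does, but it does not say which last observation it means. Two programmers could therefore code the same participant differently, and on one of the codings the steepest rebounds drop out or fall into a lower category.

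Flares are a secondary endpoint and bear directly on the safety of stopping treatment. Protocol 4.2 explains that Amendment 5 tightened monitoring after a flare that developed very quickly in a related study. The output most exposed is the count of off-treatment flares that led to NA being resumed. Any error runs one way, towards fewer and milder flares.

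**Working it through.** The plan states no figure that depends on this definition, so there is none to reproduce. The check has four parts.

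**1. The rules applied to example series.** These values are illustrations, not trial data. Derivation 1 applies, and NA restarts after the last value shown.

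| Off-treatment HBV DNA (IU/mL) | Two consecutive values needed | Last off-treatment value also counts |
|---|---|---|
| <LLOQ, 150,000 | no flare | >20,000 |
| <LLOQ, 1,000, 150,000 | >200 | >20,000 |
| <LLOQ, 5,000, 150,000 | >2,000 | >20,000 |
| <LLOQ, 1,500, 25,000, 40,000, 60,000 | >20,000 | >20,000 |

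If the footnote's last observation means the last in the study, the middle column applies. Under Protocol 6.6.2 a re-treated participant stays in follow-up, so that observation falls on NA. Even if it means the last off-treatment value, only the flag is rescued. The first series is then a Yes with no start date, because the start sentence still needs two visits. Its grade has no interval to be read from, and overlap with an ALT/AST flare cannot be computed.

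**2. How fast the rebound must be.** Inputs: restart threshold 100,000 IU/mL; routine visits every 28 days; a retest within 14 days of receiving a result above 2,000 (Protocol 6.6.2). From a previous value x over d days:

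- rise = log10(100,000/x)
- doubling time = d × ln 2 / ln(100,000/x)

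| x (at most) | d | Rise (log10) | Doubling time (at most) | Grade on the two-value reading |
|---|---|---|---|---|
| 200 | 28 | 2.70 | 3.1 days | none |
| 2,000 | 28 | 1.70 | 5.0 days | at most >200 |
| 20,000 | 28 | 0.70 | 12.1 days | at most >2,000 |
| 20,000 | 14 | 0.70 | 6.0 days | at most >2,000 |

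Missing the flare altogether thus needs about 2.70/4 = 0.67 log10 per week. Under-grading needs less.

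**3. Illustrative shares.** Assumptions: linear log10 growth from 20 IU/mL; 4-weekly visits; retests 1.5 weeks after a value above 20,000 and 2.5 weeks after one above 2,000; assay SD 0.15 log10; every retest counted; NA restarted at the first value above 100,000 with no further off-treatment sample. Repeated runs, among participants restarted on that rule, gave:

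| Slope (log10/week) | Not graded >20,000 | No virologic flare |
|---|---|---|
| 0.3 | about 10% | 0% |
| 0.5 | 42–44% | 0% |
| 0.75 | 76–78% | about 10% |
| 1.0 | 81–83% | 31–33% |

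One extra pre-dose sample half a week after the triggering value takes both columns to 0% at every slope.

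**4. ALT/AST.** The off-treatment biochemical flare needs two successive elevated visits with no study intervention. The on-treatment type needs two while receiving one. A rise with one value before restart and one after fits neither.

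**The case against.** The strongest reply is that the footnote already solves the problem. Virologic flares are assessed only off treatment, that period stops at NA restart, and the No code is conditioned on off-treatment measurements. The last observation is then naturally the last one before restart, and every series above is a Yes above 20,000. This is a fair reading and it may be the intended one. It does not remove the inconsistency. The start and grading sentences still demand two values, and the omission stands out beside the breakthrough rule, which names its period.

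Four further points stand and limit the concern.

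- A reader might infer that clinical flares also end at NA restart. They do not: a clinical flare ends at the later of its two component end dates, and an ALT/AST flare starting up to 4 weeks after the virologic flare ends still counts.
- A reader might infer that ALT/AST flares around restart are lost in general. Two elevated values after restart are captured as an on-treatment flare. The gap is one value on each side.
- A value above 100,000 also triggers a retest within 7 days of the result being received. A sample drawn before the first NA dose could supply the second value. The documents neither guarantee nor exclude it, and SAP 5.1.2 does not say whether retests in the same visit window count for flares.
- Affected participants remain visible elsewhere: NA re-treatment is summarized separately, and individual HBV DNA and ALT profiles are plotted.

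**Conclusion.** The concern holds as an internal inconsistency in a secondary-endpoint definition. As worded, it can drop a fast rebound or grade it one or more categories too low, and with no virologic flare there is no clinical flare. Whether that happens depends on how the footnote is read and on whether a pre-dose sample exists.

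It is tempting to say that these flares are missed and to quote the simulated shares as the expected loss. The documents do not support that. They give no rebound slopes and no expected number of single-value restarts, and the shares vanish with one pre-dose sample.

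For scale only: Protocol Appendix 10 reports that 19.1% met the NA completion criteria on JNJ-3989 200 mg in a related study. If that carried over, 0.191 × 24 = 4.6, or about 4 to 5 participants, would stop NA. One misclassified case would then be 20–25% of those at risk. That is conditional on a case occurring; it is not a forecast.

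**What to change.** In SAP 5.4.2.6.1:

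1. Treat a criterion as confirmed when it is met on two or more successive time points, or on the final off-treatment measurement before NA is resumed or the study ends.
2. Apply this one rule to the Yes/No flag, the start date, the peak grade (both derivations) and the off-treatment ALT/AST criterion. Remove the parenthesis that restricts the grade to two values.
3. State that unscheduled retests count as time points.
4. Assign an ALT/AST flare that starts off treatment to the off-treatment period even if the confirming value falls after restart.

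The cost is SAP wording and one programming rule; no new data are needed. The downside is that a few single high values will count as flares, so reported incidence rises slightly. A listing of participants who restarted NA after one high value would show how many. The clinical restart rule does not change.

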5.4. Secondary Endpoints Analysis

All secondary endpoints will be analyzed for the ITT set.

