5.4.2.4.7. NA Re-Treatment During Follow-up

Proportion of participants who have NA re-treatment during follow-up will be summarized.

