5.4.2.4.9. Thresholds On Multiple Markers

The number and proportion of participants who meet the following blood marker reduction/seroclearance thresholds at 12, 24, 36 and 48 weeks, respectively, after stopping all study interventions (including NA and PegIFN- α 2a) and not having NA re-treated will be summarized descriptively for each marker and each threshold listed below.

- **HBsAg<LLOQ and HBV DNA**
 - HBsAg<LLOQ and HBV DNA<LLOQ**
 - HBsAg<LLOQ and HBV DNA≥LLOQ
 - HBsAG<LLOQ and HBV<2,000 IU/ml
- **HBsAg≥LLOQ and HBV DNA<2,000 IU/ml**
 - HBsAg≥LLOQ and HBV DNA<LLOQ**
 - HBsAg≥LLOQ and HBV DNA≥LLOQ
 - HBsAg≥LLOQ and LLOQ ≤HBV DNA<2,000 IU/ml
- **HBsAg≥LLOQ and HBV DNA≥2,000 IU/ml**
 - HBsAg<100 IU/mL and HBV DNA≥2,000 IU/ml
 - HBsAg≥100 IU/mL and HBV DNA≥2,000 IU/ml
- **HBsAg<100 IU/ml and HBV DNA<2000 IU/ml**
- **HBsAg<100 IU/ml and HBV DNA<LLOQ****

** HBV DNA<LLOQ will be summarized overall. Additional analyses may assess HBV DNA<LLOQ TD versus TND.

Due to the exploratory objectives of this study, additional blood marker reduction/seroclearance thresholds may be added at a later point in time according to the clinical interest.

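### Off-treatment biochemical and clinical flares lack a not-applicable code and a stated denominator, and the HBV DNA ≥2,000 IU/mL rows omit participants re-treated for rebound

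*SAP*

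**What the plan says.** **Flare coding (SAP 5.4.2.6.1).** Virologic flare has three codes. The third sets aside participants without off-treatment data: "2 (Not applicable) = no off-treatment HBV DNA quantitative measurements available". Off-treatment biochemical flare and clinical flare have two codes only, the second being "0 (No) = otherwise". The same two-level code is used for on-treatment biochemical flare. On timing, the section states: "The virologic and clinical flares will be assessed only off-treatment, while biochemical flares will be identified on-treatment and off-treatment, respectively". On the summary it states: "The incidence rate will be calculated and summarized for each type of on-treatment or off-treatment flares (virologic, biochemical and clinical) separately". No denominator follows.

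**Analysis set.** SAP 5.4 says "All secondary endpoints will be analyzed for the ITT set". ITT (SAP Section 4) is everyone assigned or enrolled who received at least one dose; stopping NA is not required. Under SAP 5.4.2.4.6, participants who miss the NA completion criteria at Week 48 stay on NA in follow-up. Those on PegIFN may be reassessed when PegIFN ends.

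**Multiple-marker table (SAP 5.4.2.4.9).** Every row, including those for HBV DNA ≥2,000 IU/mL, is limited to participants who have stopped all interventions "and not having NA re-treated will be summarized descriptively for each marker and each threshold listed below".

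**Re-treatment.** In Protocol 6.6.2, one trigger for restarting NA reads "Immediately with an HBV DNA value of >100,000 IU/mL (irrespective of confirmation and/or ALT increase". The others are confirmed HBV DNA above 20,000 IU/mL, confirmed HBV DNA above 2,000 IU/mL with ALT above 5x ULN, confirmed HBeAg seroreversion, and signs of declining liver function. Earlier restart is at the investigator's discretion. SAP 5.4.2.4.7 adds: "Proportion of participants who have NA re-treatment during follow-up will be summarized". It gives no denominator either.

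**The concern.** An off-treatment flare can occur only in someone who is off treatment. If participants who stay on NA throughout follow-up are coded No, they enter the percentage as event-free although they were never at risk. Clinical flare is also inconsistent with its own component. It requires a virologic flare, so a participant who never stops NA is not applicable for the component and No for the composite.

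In the multiple-marker table, requiring no re-treatment makes sense for favourable rows, because HBV DNA suppressed by restarted NA is not off-treatment control. For the HBV DNA ≥2,000 IU/mL rows the same condition removes participants largely because they had the outcome that the row describes.

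The question matters here because flares are a listed secondary endpoint and the study stops NA in selected participants. Protocol 4.2 describes closer monitoring introduced after a severe flare following NA discontinuation in another study, and Protocol 2.3.3 cites a case of post-treatment reactivation with subacute hepatic failure. A reader will want the risk among those who stopped.

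**Working it through.** The plan states no expected flare, rebound or re-treatment rate, so there is no figure to reproduce. The calculations below are direct proportions on assumed counts.

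**1. Flare denominator**

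Inputs:
- N = 24, the target for Panels 1 and 2 (SAP 1.2).
- k = number who stop all interventions. This is not given. Protocol Appendix 10 (rationale for Amendment 4) reports that 19.1% met the NA completion criteria at Week 48 on the 200 mg dose in another phase 2b study of the compound. 0.191 × 24 = 4.58, taken as 5. Shares of 10%, 40% and 60% give k = 2, 10 and 14 after rounding.
- f = number with an off-treatment flare, assumed.

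Rate among those at risk = f/k. Rate with ITT as denominator = f/N. Their ratio is (f/N)/(f/k) = k/N, whatever f is.

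| Flares (k = 5) | f/k | f/24 |
|---|---|---|
| 1 | 20.0% | 4.2% |
| 2 | 40.0% | 8.3% |
| 3 | 60.0% | 12.5% |

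The ratio is 5/24 = 0.21. For the other shares it is 2/24 = 0.08, 10/24 = 0.42 and 14/24 = 0.58. If the denominator is instead the participants who came off treatment, the ratio is 1 and nothing is diluted.

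On-treatment biochemical flare is unaffected, because every ITT participant was dosed and so was at risk on treatment.

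**2. HBV DNA ≥2,000 IU/mL rows**

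Let k participants have stopped, b of them rebound to ≥2,000 IU/mL, and t of those b be re-treated before the time point. Keeping the re-treated as rebounders gives b/k. Dropping them from the numerator only gives (b − t)/k. Dropping them from both gives (b − t)/(k − t). The SAP does not say which of the last two applies.

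With k = 10 and b = 4, so b/k = 40%:

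| t | (b − t)/k | (b − t)/(k − t) |
|---|---|---|
| 2 | 2/10 = 20% | 2/8 = 25.0% |
| 3 | 1/10 = 10% | 1/7 = 14.3% |
| 4 | 0% | 0% |

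The direction is not guaranteed. If 1 of the 4 rebounders and 2 of the 6 non-rebounders are re-treated and all three leave both counts, the row shows 3/7 = 42.9% against 40%.

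**The case against.** The strongest reply on flares is that dilution needs an ITT denominator and the SAP never writes one. The definitions already confine off-treatment biochemical flare to time without study interventions, and clinical flare is assessed only off-treatment, so a programmer could reasonably use those who stopped. This stands in part: dilution is the literal reading, not a stated result. But where the SAP wants a restricted denominator it says so, for example ALT normalization only in those with elevated ALT at baseline (5.4.2.4.5) and HBeAg seroclearance only in those HBeAg positive at entry (5.4.2.3). Here it is silent, the general rule is ITT, and the code gives everyone a value. At best the rate is undefined.

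On the multiple-marker table, the reply is that it shows off-treatment marker status at fixed times and is not a rebound analysis. Rebound and re-treatment appear elsewhere: virologic flares graded by peak above 200, 2,000 and 20,000 IU/mL up to NA restart, flares followed by re-treatment by type, the re-treatment proportion, individual HBV DNA plots, and a listing of flares with liver decompensation. This largely stands. A reader might infer that rebound is understated throughout the report or that severe rebounds disappear from it; these summaries show otherwise. The gap that remains is narrower. The re-treatment proportion has no stated denominator, so it cannot safely be set beside the 5.4.2.4.9 rows. Peak grading also asks for two consecutive values, while one restart trigger applies without confirmation; only the allowance for the last observed time point may recover such a case.

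It is also fair that the counts above are invented, that 19.1% is another study's result, and that participants on PegIFN may stop NA later, so the share who stop here is unknown.

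**Conclusion.** Two limited points hold.

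First, off-treatment biochemical flare and clinical flare lack the not-applicable code that virologic flare has, and no denominator is given. Under the literal ITT reading the reported rate is k/N times the rate among those at risk: 0.21 if 5 of 24 stop, and 0.08 to 0.58 if 10% to 60% stop. These factors rest on the ITT reading and on an assumed share.

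Second, the HBV DNA ≥2,000 IU/mL rows of SAP 5.4.2.4.9 leave out participants re-treated because of rebound. These rows read low whenever rebounders are re-treated more often than non-rebounders. The Protocol 6.6.2 triggers make that likely but not certain, since re-treatment can have other causes. The effect is confined to that table.

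A reader might also infer that the plan fixes different denominators for virologic and biochemical flares. It does not: virologic flare is split into two derivations by last on-treatment HBV DNA, with no denominator stated for either.

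This should be fixed, but it is not critical. The summaries are descriptive and secondary in an exploratory study without hypothesis tests, and neither the primary endpoint nor participant management is affected.

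**What to change.** In SAP 5.4.2.6.1:
- For off-treatment biochemical flare, add code 2 (not applicable) for participants with no off-treatment ALT/AST measurement.
- For clinical flare, add code 2 for participants with no off-treatment ALT/AST or no off-treatment HBV DNA measurement.
- Leave on-treatment biochemical flare as it is.

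Report off-treatment flares and NA re-treatment (5.4.2.4.7) as n/N on one common denominator, the participants who stopped all study interventions, and show beside it how many have off-treatment data.

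In SAP 5.4.2.4.9, add a row for NA re-treated by this time point on the same denominator. The three mutually exclusive main categories (HBsAg <LLOQ; HBsAg ≥LLOQ with HBV DNA <2,000 IU/mL; HBsAg ≥LLOQ with HBV DNA ≥2,000 IU/mL), plus re-treated, plus missing or not reached, should then sum to all who stopped. The sub-rows overlap and need not sum.

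The cost is SAP wording and table-shell work; no clinical rule changes. Compared with an ITT denominator, the reported flare percentages will be higher and will rest on small denominators, so the counts should always be shown with them.
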